#### **10.2.1 Key Secondary Estimand**

The treatment condition and population of the estimand for key secondary endpoints is the same as for the primary endpoint. The variable in each case will be the mean change from baseline through Week 16 in each parameter. Also, in each case, the population level summary will be the arithmetic mean change.

### **10.3 Analysis of Other Secondary Endpoints**

Biomarkers of lipid metabolism, glycemic control and novel biomarkers of kidney function as well as weight will also employ a model similar to the primary endpoint except for the

concentration of CSL346 in urine. The analysis for continuous endpoints is an MMRM analysis of change from baseline to each post-baseline measurement (Weeks 4, 8 and 16). The model will include treatment, stratification related to the concomitant use of SGLT2i, visit (as a categorical factor), and interactions between visit and each of the other model terms, as well as the corresponding baseline measurement as a covariate (refer to [Section 16.1](#) for respective SAS code). Treatment comparisons of interest will be similar to that of the primary endpoint. Lipid parameters will be natural log transformed prior to analysis.

Urinary biomarkers will be normalized for urine creatinine. These urinary biomarkers include urinary VEGF-A, soluble VEGF receptor 1 (VEGF-R1), kidney injury molecule-1 (KIM-1), neutrophil gelatinase-associated lipocalin (NGAL), clusterin, and monocyte chemoattractant protein-1 (MCP-1) and epidermal growth factor (EGF). Normalization is performed by dividing the urinary biomarker by urine creatinine collected at the midstream morning void taken the same day as the urinary biomarker. Normalized urinary biomarkers should be reported in units of pg/ $\mu$ g. To obtain these units, first convert urinary creatinine from units of mg/dL to units of  $\mu$ g/mL by multiplying by 10. Then divide the urinary biomarker (pg/mL) by urinary creatinine ( $\mu$ g/mL) to get normalized results with units of pg/ $\mu$ g.

A repeated measures analysis of covariance model will be employed to analyze the concentration of CSL346 in urine, collected at Day 1, Day 8, and Day 85. The repeated measures analysis of covariance model will include terms for treatment, baseline as a covariate and SGLT2i use.

All analyses for biomarker will be performed on the PD Analysis Set. Analyses for KIM-1, NGAL, EGF and MCP-1 will be performed in addition for the PP Analysis Set. Analyses for urine CSL346 concentration will be performed on the ITT Analysis Set.

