10.3.4 Pharmacokinetic Analyses

Secondary Endpoints

Serum concentrations of CSL346 will be listed by individual subject and will be summarized by dose level and nominal time point using descriptive statistics (ie, n, arithmetic mean, SD, CV%, median, geometric mean, geometric CV%, minimum, and maximum). Individual subject CSL346 serum concentration versus time will be plotted on linear and semilogarithmic scales. The C_{trough} of CSL346 will also be summarized visually, by dose level.

PK parameters will be derived using noncompartmental analyses, and will include the following:

- C_{\max} after IV loading dose
- T_{\max} after IV loading dose
- C_{\max} after first SC dose
- T_{\max} after first SC dose
- $AUC_{0-\tau}$
- C_{trough} after each dose

The following descriptive statistics will be presented, by dose level, for all PK parameters, except for T_{\max} , n, arithmetic mean, SD, CV%, median, geometric mean, geometric CV%, minimum, and maximum. The n, median, minimum, and maximum will be summarized for T_{\max} . Additional information on the analyses of PK parameters will be provided in the SAP. These analyses will be performed on the PK Analysis Set.

Dose-adjusted PK exposure parameters will be natural log transformed and analyzed in an analysis of variance model, comparing the 16 mg/kg and 8 mg/kg dose levels. The estimate and 90% CI for the difference of 16 mg/kg – 8 mg/kg will be exponentiated to obtain the point estimate and CI for the geometric mean ratio. The point estimate and CI will be used to assess dose proportionality.

Exploratory Endpoint

Urine concentration of CSL346 will be listed by individual subject and will be summarized by nominal time point using descriptive statistics. This analysis will be performed on the PK Analysis Set.

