### **6.2 Intent-to-Treat Analysis Set**

The Intent-to-Treat (ITT) Analysis Set comprises all subjects who were randomized. The ITT analysis set will be analyzed using the treatment to which the subject was randomized, regardless of the treatment actually received. The ITT analysis set will be used in the analysis of the primary endpoint. Any subject who receives a treatment randomization number will be considered to have been randomized.

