### 6.5 Pharmacokinetic Analysis Set

The PK Analysis Set comprises all subjects who receive an infusion of CSL346 with at least 1 quantifiable concentration of CSL346 after administration. The actual treatment will be used for subjects in this analysis set.

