## 12 Pharmacokinetic Analyses

The PK analysis will be performed using the PK Analysis Set.

All non-compartmental analyses are to be performed according to CSL SOP PK-GDL-01 and will be performed by CSL Behring Clinical Pharmacology & Pharmacometrics by using WinNonlin® version 8.1 or later. Alternatively CSL Behring may contracting a Clinical Research Organisation to derive the PK parameter.

After data base lock, CSL Behring Clinical Pharmacology & Pharmacometrics will produce all SDTM domains needed for the PK analysis (serum PK analysis). The PC domain containing the CSL346 concentrations, nominal blood sampling times, actual sampling time relative to the start of the dosing, and actual dosing and the PP domain containing the PK parameters will be provided. Any CSL346 serum concentrations which will have been excluded from the derivation of the PK parameters will be flagged in the data.

Parexel will produce the TFLs for the CSL346 serum concentrations and the PK parameters as specified below.

Population PK analyses will be performed according to the Modeling and Simulation Analysis Plan and reported separately.

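### The SAP's model for urine CSL346 concentration is mis-specified: it includes placebo subjects, names an unscheduled Day 1 sample and lists no visit term

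*SAP*

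**What the plan says.** SAP Section 10.3 fits a repeated measures analysis of covariance to urine CSL346, "collected at Day 1, Day 8, and Day 85". The model is to "include terms for treatment, baseline as a covariate and SGLT2i use". No visit term, covariance structure or treatment contrast is named for it. On the analysis set: "Analyses for urine CSL346 concentration will be performed on the ITT Analysis Set". SAP Section 6.2 defines that set: "The Intent-to-Treat (ITT) Analysis Set comprises all subjects who were randomized".

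Other parts of the plan differ:

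- **Protocol Section 10.3.4** has urine concentration "summarized by nominal time point using descriptive statistics. This analysis will be performed on the PK Analysis Set".
- **SAP Section 12** opens with "The PK analysis will be performed using the PK Analysis Set", and Section 12.1 summarizes urine concentration descriptively by nominal time point. SAP Section 6.5 defines the set: "The PK Analysis Set comprises all subjects who receive an infusion of CSL346 with at least 1 quantifiable concentration of CSL346 after administration". Placebo subjects are therefore outside it.
- **Sampling.** Protocol Tables 7 and 9 and the Schedule of Assessments (repeated in SAP Appendix 16.8) place the 24-hour urine at Screening Visit 1 (labelled Baseline), Visit 5 (Day 8) and Visit 9 (Day 85).
- **SAP Section 5** lists two departures from the protocol: the per-protocol set definition and the removal of VEGF-B.

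**The concern.** Urine CSL346 is an exploratory endpoint (protocol Section 2.3.2, SAP Section 4.1.4). The related objective is to measure the drug in urine and explore its association with albuminuria. A model that includes placebo mainly asks whether an administered antibody is more abundant in people who received it, which does not serve that objective.

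The placebo values also have essentially no spread. If they share a residual variance with the active arms, they pull the estimate down or distort it, and SEs for some contrasts become wrong.

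The unscheduled Day 1 sample and the missing visit term mean that two programmers could implement the paragraph differently. Because the model is not declared in Section 5, a reader comparing the protocol with the report would not learn that it had been added.

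**Working it through.** **The plan's own figures.** None is stated for the urine model. The only design figures concern the primary endpoint, and they reproduce. With SD 0.65, difference 0.315, one-sided alpha 0.10 and 85% power, n per arm = 2 × (1.2816 + 1.0364)² × 0.65² / 0.315² = 45.8, so 46 per arm or 92 in all, close to the stated 94. At 47 per arm the power is 85.7% (normal) or 85.5% (t), and 94/0.94 = 100. They are used here only for the planned arm sizes of 25 / 25 / 50.

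**Assumptions.** The documents give no SD for urine CSL346, no below-quantification (BLQ) rule for the urine model and no covariance structure. I take placebo values as zero, one residual variance pooled over arms, and a 16:8 mg/kg SD ratio r from 1 to 3, with the 8 mg/kg SD set to 1. The calculation is for a one-way comparison of arms.

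**Formulas.** Pooled variance: V = (24 × 1 + 24 × r² + 49 × 0) / 97. For a contrast with coefficients c, the model variance is V × Σ(c²/n) and the true variance is Σ(c² × SD²/n). The SE ratio is the square root of model over true.

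For r = 1, V = 48/97 = 0.495:

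- Each dose versus placebo: √[0.495 × (1/25 + 1/50) / (1/25)] = √(0.495 × 1.5) = 0.862.
- 16 versus 8 mg/kg: √[0.495 × (2/25) / (2/25)] = √0.495 = 0.703.
- Combined versus placebo: √[0.495 × (0.25/25 + 0.25/25 + 1/50) / (0.25/25 + 0.25/25)] = √(0.495 × 2) = 0.995.

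For r = 2, V = 120/97 = 1.237; for r = 3, V = 240/97 = 2.474.

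| Model SE / true SE | r = 1 | r = 2 | r = 3 |
|---|---|---|---|
| 8 mg/kg vs placebo | 0.862 | 1.362 | 1.926 |
| 16 mg/kg vs placebo | 0.862 | 0.681 | 0.642 |
| 16 vs 8 mg/kg | 0.703 | 0.703 | 0.703 |
| Combined vs placebo | 0.995 | 0.995 | 0.995 |

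With 124 randomized (31 / 31 / 62), every ratio is within 0.002 of these.

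**Error rate for 16 versus 8 mg/kg, if tested.** At a nominal one-sided 10% level, 1 − Φ(1.2816 × 0.703) = 0.184. A simulation of 20,000 trials with equal active-arm SDs gave 0.368 at a nominal two-sided 0.20. The same test restricted to the 25 + 25 treated subjects gave 0.201, and its SE ratio is 1.00.

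**Baseline covariate.** The sample precedes any dose, so values below the urine limit of 80 ng/mL (SAP Section 12.1) are expected in all arms. An all-zero column is aliased with the intercept. A fit with and without it gave the same rank (4), the same estimate and the same SE (0.0909).

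**Day 1.** If the Screening value were entered as a Day 1 response of zero and no visit term were fitted, a constant difference d at Days 8 and 85 would average to (0 + d + d)/3 = 2d/3. An unstructured covariance over the three times would be singular (rank 2 of 3).

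**The case against.** The strongest reply has four parts.

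**The protocol's analysis is kept.** SAP Section 12.1 retains the descriptive summary under the PK Analysis Set, so the model is an addition. This is correct. A reader might infer that the SAP replaced the protocol's plan, and it did not. The addition is still undeclared and on a different set.

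**A model with placebo has some protocol basis.** Protocol Section 10.3.7 gives exploratory endpoints a general repeated measures model with treatment, SGLT2 stratum and baseline, on the PD Analysis Set, which includes placebo. That section does not name urine CSL346, Section 10.3.4 is more specific, and neither specifies ITT.

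**The SE fault is conditional.** A reader might infer that the model's standard errors are wrong throughout. The documents do not support that. Only the placebo values can distort them, and only if the variance is pooled. The combined comparison, which is the primary-type contrast, is within 0.5% because combined and placebo arms are equal in size. The baseline covariate leaves the SE unchanged. The 16 versus 8 mg/kg contrast, where inflation would be clearest, is not named for urine in Section 10.3, and urine CSL346 is absent from the one-sided test table in Appendix 16.9.

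**Day 1 may be a label slip.** The protocol calls the Visit 1 urine sample Baseline, and SAP Section 14 plots urine concentration at Days 8 and 85 only. That is plausible, but the text still needs correcting.

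**Conclusion.** The urine CSL346 paragraph in SAP Section 10.3 is mis-specified and should be corrected. Four faults rest on the text alone: an analysis set that conflicts with protocol Section 10.3.4 and SAP Section 12, a Day 1 sample that no schedule contains, no listed visit term in a repeated measures model, and no entry in Section 5. The baseline covariate is uninformative but harmless to the SE. That it is below quantification in everyone is an inference from its pre-dose timing; the BLQ rules in Section 12.1 are written for serum summaries.

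The numerical consequence depends on zero placebo values and a pooled variance, neither of which the SAP states. Under them the single-dose SEs are mis-sized in either direction, depending on an SD ratio that the documents do not give. The 16 versus 8 mg/kg SE would be about 30% too small if that contrast were tested. Combined CSL346 versus placebo would be sized correctly but would tell the reader nothing useful. This affects one exploratory endpoint and leaves the primary analysis untouched.

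**What to change.** Choose one of two options.

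1. Delete the urine model from SAP Section 10.3 and rely on the descriptive PK-set summary already in Section 12.1.
2. Keep a model, but in the PK Analysis Set only. Compare 16 with 8 mg/kg at Day 8 and Day 85, with visit and dose-by-visit terms, no baseline covariate and no Day 1. State the covariance structure. State how urine values below 80 ng/mL are handled before any log transformation, since the log of zero is undefined.

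Under option 2, list the model in SAP Section 5 as an addition to the protocol's plan. The cost is one SAP paragraph and at most one line in Section 5. No data collection, sample size or primary analysis changes.

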#### **10.4 Missing Data and Imputation**

To avoid missing data with regard to the primary endpoint, ACR, procedures will be in place to maximize the ability to collect first morning voids for every subject at every planned visit. Likewise, every attempt will be made to retain subjects in the study once they are randomized. Therefore, it is anticipated that missing data with regard to the primary endpoint will be kept to a minimum. Imputation is only being considered for the sensitivity analysis for the primary endpoint.

#### **10.5 Treatment Compliance**

The calculation of overall compliance is based on receiving all four injections of IP. An injection of at least 80% of the planned volume will satisfy the criteria of receiving a

compliant injection at each of the 4 visits. The following summaries will be provided by treatment group:

- The number of subjects receiving all four doses of IP;
- The number of subjects receiving at least 80% of the planned infusion volume at each visit.

Compliance will be summarized for the Safety Analysis Set.

A by-subject listing will be provided including:

- By injection: the randomized and actual treatment administered, planned and actual volume of IP, individual and categorized compliance;
- Overall (across all injections): cumulative planned and cumulative actual volume of IP, individual and categorized compliance, number of injections.

Calculation of compliance and extent of exposure (as described in Section 11.1) will be based on drug accountability data collected by eCRF.

## 11 Safety Analyses

The safety analyses will be based on the Safety Analysis Set as defined in [Section 6.3](#) and on the treatment which the subject received.

### 11.1 Extent of Exposure

Exposure to the IP will be descriptively summarized by treatment group:

- Number of subjects receiving loading dose;
- Summary statistics for Loading dose received;
- Number of subcutaneous infusions administered per visit and overall;
- Summary statistics for Total dose received [mg/kg] per visit and overall;
- Summary statistics for Total volume received (ml) per visit and overall.

Total dose received [mg/kg] will be provided with the study data. The listing of individual subject data will include all variables presented in the summary tables.

### 11.2 Adverse Events

AEs will be coded using the MedDRA dictionary (the MedDRA version will be populated in the tables output). AEs will start to be collected upon subject's signing of the informed consent form (ICF). AEs observed during the screening and lead-in periods of the study will be summarized separately as no treatment is received during this time. TEAEs, defined as AEs starting on or after the date of the first administration of the IP (IV loading dose),

through the end of the follow up period will be summarized. All AE tables will summarize the number and percentage of subjects with TEAEs for each of the three randomized treatment groups, for a combined column for the two CSL346 groups, as well as an overall column. All AEs regardless of whether they were treatment-emergent or not will be listed.

Where AE start dates are missing or partially missing, AEs will be assumed to be treatment-emergent, except if the partial start dates or the AE end date indicate that the AE started before the first administration of the IP (IV loading dose) during the treatment period (Section 4).

**Table 2 TEAE Assignment in Case of Missing AE Start Date Elements**

Missing elements of AE start	Rule	
Regardless of any missing information for AE start: AE end date / time < IP start date / time		non-TEAE
Otherwise (i.e., if AE end date / time $\geq$ IP start date / time)		
- all		TEAE
- day and month	AE start year $\geq$ IP start year	TEAE
	AE start year < IP start year	non-TEAE
- day	AE start month / year $\geq$ IP start month / year	TEAE
	AE start month / year < IP start month / year	non-TEAE
- time	AE start date $\geq$ IP start date	TEAE
	AE start date < IP start date	non-TEAE

If AE start dates or end dates are missing or partially missing for an AE, no duration will be calculated. If for a TEAE the relationship to study treatment is missing the worst case will be assumed for summarizing analysis (i.e. the relationship to study treatment will be assumed to be “Related”). A missing severity for a TEAE will be assumed for summaries as “Severe”. For non-TEAEs no imputation will be done in case of missing study treatment relationship or severity. No other imputations for missing AE information will be done.

The AESIs for this study are defined as:

- Injection site reactions (PTs as identified through a standard MedDRA query, provided by CSL Behring);
- Increase in serum creatinine, defined as a confirmed increase in serum creatinine from baseline of  $\geq 0.3$  mg/dL;

- Albuminuria, defined as a confirmed increase in urinary ACR of > 2-fold increase (doubling) from baseline with additional evidence suggesting Acute Kidney Injury (AKI);
- Increased blood pressure, defined as an observed SBP  $\geq 180$  mmHg and/or DBP  $\geq 120$  mmHg or an increase from Baseline in either SBP or DBP  $\geq 20$  mmHg and greater than 160/105 mmHg;
- A cardiac event will be defined as any clinically-meaningful change from Baseline in cardiac-related parameters, such as electrocardiogram (ECG) intervals, cardiac troponin levels [Thygesen et al, 2018], or left ventricular ejection fraction (LVEF), as reported in the cardiac AESI-specific eCRF.

For tabulated summaries injection site reactions, increase in serum creatinine, albuminuria, and increased blood pressure and cardiac events will be identified in the eCRF as marked by the investigator.

An overview summary of TEAEs, including number and percentages of subjects as well as the number of events, will be provided including the following:

- Any TEAE;
- TEAEs related to study treatment;
- TEAEs leading to discontinuation of study treatment (obtained from AE eCRF);
- TEAEs leading to study withdrawal (obtained from “End of Treatment” or “Conclusion of Subject Participation” eCRF);
- TEAEs leading to dose interruptions;
- TEAEs by maximum severity (without number of events or TEAE rate);
- Treatment-emergent AESIs;
- Serious TEAEs;
- Serious TEAEs related to study treatment;
- Fatal TEAEs.

The above overall AE table will also be provided for the whole study, for the Treatment Period and for the Follow-up Period, and for Follow-up Period separately. In addition, the overview table will be stratified by SGLT2i as well as ACR and eGFR status separately at baseline.

The following frequency tables will be generated for TEAEs, including number and percentages of subjects and the number of events:

- TEAEs by SOC and PT;
- TEAEs by PT;

- TEAEs by PT through Week 16;
- TEAEs by PT from Week 16 through Week 24;
- TEAEs by PT, stratified by SGLT2i;
- TEAEs by PT, stratified by baseline eGFR (<60 and eGFR≥60 mL/min/1.73m^2);
- TEAEs by SOC, PT, and maximum severity (without number of events);
- Related TEAEs by SOC and PT;
- Related TEAEs by PT;
- Treatment-emergent AESIs by PT;
- Serious TEAEs by SOC and PT;
- Related serious TEAEs by SOC and PT;
- TEAEs with result in drug discontinuation;
- TEAEs related to COVID-19 infection.

AEs will be presented in summaries by decreasing overall frequency (overall frequency as the number of subjects with that AE). In case of two AEs having the same overall frequency, the AEs will be ordered alphabetically.

The following by-subject listings will be provided:

- All AEs;
- SAEs;
- AEs leading to study withdrawal or permanent discontinuation of study treatment;
- AESIs by type of AESI.

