If, after Step 2, the subject continues to have mild injection site reactions that are deemed unacceptable by the subject or Investigator, and would otherwise lead to discontinuation of the IP, contact the Study Medical Monitor to discuss and document the appropriate action to be taken for that subject. If the Medical Monitor approves, then move to Step 3 and discontinue further dosing with IP. Every effort should be made to continue the subject's participation in Follow-up Visits even if the IP is discontinued.

For any injection site reaction that exceeds the definition of mild, either in duration or severity of symptoms, the Study Medical Monitor must be contacted to discuss and document the rationale for continuing administration of the IP at a decreased total SC infusion volume and / or dose, or discontinuing further dosing.

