The trending changes in SCr over multiple time points will be evaluated in the context of changes in albuminuria, BP, and other clinical parameters over that period, and recommendations will be provided to the Investigator. This may include guidance for heightened monitoring of renal parameters, clinical maneuvers to reverse reversible causes of AKI not related to IP (eg, treat active urinary tract infection), temporary interruption of IP, or permanent discontinuation from IP. The Medical Monitor will be available 24 hours a day and must be consulted by the Investigator; subsequently, the Investigator will make the decision to either administer the next monthly dose of IP or permanently discontinue a subject from treatment. Note that every effort will be made to continue the subject's participation in Follow-up Visits even if IP administration is stopped.

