### **Study Treatment Discontinuation or Study Discontinuation**

Subjects who have either study treatment discontinuation or study discontinuation due to

COVID-19 will have the reason captured in the electronic case report form (eCRF). On the appropriate eCRF form to record either study medication discontinuation (“End of Treatment” form) or study discontinuation (“Conclusion of Subject Participation” form), a reason will be selected which includes a field for descriptive text. The reason can be either “Withdrawal by Subject”, “Physician Decision” or “Other”. The associated free text field entry will include “COVID-19”. When either treatment or the study is discontinued due to an AE or death, the specific corresponding AE is collected. Discontinuations due to COVID-19 adverse events (AE) will then be identified based on whether the Medical Dictionary for Regulatory Activities (MedDRA) code for the AE is included in the COVID-19 standard MedDRA query (SMQ) (Narrow).

Cases of study treatment discontinuation or study discontinuation due to COVID-19 will be included in the summary of subject disposition.

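### The adverse-event overview counts a stop of study drug as a study withdrawal, because its source rule accepts the End of Treatment form as well as the Conclusion of Subject Participation form

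*SAP*

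**What the plan says.** SAP 11.2 (Adverse Events) lists the rows of an overview table of treatment-emergent adverse events (TEAEs). Two of them matter here, and each names its data source:

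- The row for stopping of treatment reads "TEAEs leading to discontinuation of study treatment (obtained from AE eCRF", so it rests on a single form.
- The row for leaving the study begins "TEAEs leading to study withdrawal (obtained from" and then lists two forms as alternatives: the End of Treatment form, and the form called Conclusion of Subject Participation.

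SAP 7.1, under study treatment discontinuation or study discontinuation, says what the two forms in the second row are for. They "record either study medication discontinuation (“End of Treatment” form) or study discontinuation (“Conclusion of Subject Participation” form". The same paragraph adds: "When either treatment or the study is discontinued due to an AE or death, the specific corresponding AE is collected".

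The protocol keeps the two outcomes apart. In section 9.1.3.2, on serum creatinine, "every effort will be made to continue the subject's participation in Follow-up Visits even if IP administration is stopped". Section 9.1.3.1, on injection site reactions, likewise asks for continued "participation in Follow-up Visits even if the IP is discontinued". Sections 9.1.3.3 (albuminuria) and 9.1.3.4 (blood pressure) carry equivalent requests. Section 9.1.3.5 sends subjects whose IP is stopped for a cardiac event into the Follow-up Period.

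**The concern.** A study-withdrawal row should show how many subjects left the study because of an adverse event. The overview already has a separate row for subjects whose treatment was stopped. If the withdrawal row also accepts the form that records stopping of treatment, it no longer isolates departures from the study.

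The subjects affected are expected by design: each of the five categories of adverse event of special interest has a route by which IP is stopped and the subject remains under observation. A reader of the safety section could conclude that adverse events drove people out of the study when they only ended dosing. The same report could then show a different number in the disposition table.

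**Working it through.** The plan states no figure to reproduce. The check sets the source rule beside the form definitions and follows one subject through them.

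**Step 1. What each form records (SAP 7.1).** End of Treatment: study medication stopped. Conclusion of Subject Participation: study stopped. For either, if the reason is an adverse event, the specific event is collected.

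**Step 2. A subject the protocol expects.** The subject stops IP early because of a TEAE, stays in follow-up, and attends Week 16 and Week 24.

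| Where | What is recorded or counted |
|---|---|
| End of Treatment form | IP stopped, linked to the event |
| Conclusion of Subject Participation form | No early departure |
| SAP 9.1 disposition | Completed Week 16 and Week 24 |
| SAP 11.2 withdrawal row, either form accepted | Counted as a withdrawal |
| SAP 11.2 withdrawal row, Conclusion form only | Not counted |

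The fourth line contradicts the third.

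**Step 3. Size of the error.** Let A be the subjects with a TEAE as the reason on the End of Treatment form, and B those with a TEAE as the reason on the Conclusion form. The written rule counts A or B; the intended count is B. The excess is the number of subjects in A but not in B, chiefly those who stopped IP for a TEAE and stayed. The documents give no value for it.

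**Step 4. Weight of one subject.** Planned arm sizes are in Protocol 10.1.

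- One CSL346 dose arm: 1/25 = 4 percentage points.
- Placebo, or both CSL346 arms combined: 1/50 = 2 percentage points.
- If 124 were randomized 1:1:2, each dose arm would have 124/4 = 31 subjects, and 1/31 = 3.2 percentage points.

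**Step 5. Where it spreads.** SAP 11.2 repeats the overview by study period and by SGLT2 inhibitor use, baseline ACR and baseline eGFR. The same misclassification recurs there, with smaller denominators in the subgroups.

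**Step 6. Whether disposition would explain the gap.** SAP 9.1 tabulates treated subjects who left the study before Week 16 and before Week 24, with reasons. It lists no general row for premature stopping of IP, although Protocol 10.3.1.1 does. A reader comparing the two tables would see a mismatch without the row that accounts for it.

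**Step 7. Whether this is an isolated slip.** SAP 10.1.2 identifies pandemic-related treatment discontinuation from the Conclusion of Subject Participation form, which is the reverse mix-up. The two forms are not kept apart consistently in the SAP.

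**The case against.** The best defence is that *or* may be loose wording for whichever form holds the withdrawal reason. The case report form is not among the documents, so a study-withdrawal field on the End of Treatment form cannot be excluded. SAP 7.1 describes the forms only in its COVID-19 section, and SAP 3 places implementation details in a separate document. This limits certainty about what would be programmed. It does not rescue the text: SAP 7.1 gives the End of Treatment form one purpose, and that purpose is not study withdrawal.

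Several stronger conclusions are tempting, and the documents do not support them.

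- *The row comes from the End of Treatment form alone.* It does not; the rule mixes two forms.
- *The over-count could reach 6 of 100, or 30 of 124 (124 − 94).* These figures come from the 6% drop-out assumption and the 94-completer target in Protocol 10.1. They describe subjects who drop out or fail to complete, not subjects who stop IP for a TEAE and stay. A drop-out who leaves because of a TEAE is a true withdrawal. A subject who stops IP but still provides the Week 16 ACR need not be a drop-out at all.
- *The two overview rows become indistinguishable.* They have different sources and can differ. A subject who received every dose and left during follow-up because of an adverse event would be expected only in the withdrawal row.
- *A headline tolerability result or a stopping rule is affected.* The adverse-event overview in Protocol 10.3.3 does not list study withdrawal. The secondary endpoint in Protocol 2.2.2 is summarized by IP discontinuation. The criteria in Protocol 3.7 do not use this row, and the committee's output has its own analysis plan (SAP 4.5.2).
- *The treatment-discontinuation row is also wrong.* Nothing shows an error in taking it from the adverse-event form.

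It also stands that true study discontinuations, with reasons, remain available in SAP 9.1, so a careful cross-check could detect the error.

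**Conclusion.** The rule is wrong as written. SAP 11.2 accepts, as evidence of leaving the study, a form that SAP 7.1 reserves for stopping study medication. The study-withdrawal row is therefore overstated by the number of subjects who stop IP for a TEAE and remain under follow-up. That number is unknown and could be zero.

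The conclusion rests on two assumptions: that *or* means either form is sufficient, and that the forms work as SAP 7.1 describes. The consequence is a potentially misleading descriptive safety row, with its repeats, and a possible conflict with disposition. The matter is small but worth correcting, because the contradiction lies within the SAP itself.

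**What to change.** In SAP 11.2, name the Conclusion of Subject Participation form as the only source for the study-withdrawal row. Leave the treatment-discontinuation row on the adverse-event form.

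The change is safe on either reading of *or*. If every study withdrawal is recorded on the Conclusion form, as SAP 7.1 says, nothing is lost by dropping the other form. If *or* would have been programmed literally, the over-count is prevented. A short check of the case report form should confirm that no study-withdrawal reason is held only on the End of Treatment form.

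The cost is one line of SAP text and the matching table specification, with no new data. If the SAP can no longer be amended, the change can be recorded as a deviation in the clinical study report, as SAP 3 provides.
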